Informed Consent	X						
Inclusion/Exclusion Criteria ^a	X	X					
Demographics/Medical History	X						
Complete Physical Exam	X						X
Brief Physical Exam			X	X	X	X	
Height	X						
Weight	X	X	X	X	X	X	X
Orthostatic Vital Signs ^b	X	X	X	X	X	X	X
12-lead ECG	X	X	X	X	X	X	X
Labs and Urinalysis	X		X	X	X	X	X
Pregnancy Testing ^c	X	X	X	X	X	X	X
In-clinic IP/Placebo Dosing ^d			X	X	X		
In-clinic Levodopa Dosing		X	X	X	X	X	X
Levodopa PK Draws ^e		X ^e	X ^e	X ^e	X ^e	X ^e	X ^e
IP/Placebo Dispense		X	X	X			
IP/Placebo Collection and Accountability			X	X	X	X	X

Commented [A1]: Confirm whether +/- 8 days or only +8 days

CONFIDENTIAL

19April21 7.0

	Visit 1 Screening	Visit 2 Randomization	Visit 3 Follow-Up	Visit 4 End of Treatment	Visit 5 End of Placebo	Visit 6 End of Study	Early Termination
	Day -21	Day 1 (+/-8 days)	Day 11 (+/- 3 day)	Day 26 (- 2 days)	Day 39 (+/- 8 days)	Day 69 (+/- 8 days)	
Instructions to Discontinue Laxatives and other BM Medications	X						
Dispense Rescue Medications ^f	X	X	X	X	X		
Stool Diary Instruction/Review ^g	X	X	X	X	X	X	X
AE Review	X	X	X	X	X	X	X
Prior and Con Meds	X	X	X	X	X	X	X
Rome IV questionnaire	X						
MDS-UPDRS ^h	X		X	X	X	X	X
C-SSRS	X	X	X	X	X	X	X
BDI-II	X		X	X	X	X	X
MMSE	X		X	X	X	X	X
SAPS-PD, Hallucination/Delusion Questionnaire ⁱ	X	X	X	X	X	X	X
PAC-QOL and PAC-SYM		X	X	X	X	X	X
Dispense Stool Collection Kits	X		X				
Collect Stool Sample ^j		X		X			X

CONFIDENTIAL**19April21_7.0**

a. Confirmation of eligibility: To be randomized to receive double-blind study medication in this study, subjects must meet the following criteria:

- Have had at least 11 "Available Data Days" (days with electronic diary compliance sufficient for determining whether a BM occurred)
- Have had <3 CSBMs/week based upon the average CSBM rate during the first 2 screening weeks (baseline period).
- Be approved for randomization by the enrollment committee

b. Three sets will be taken. Time points to be defined. Orthostatic vital signs will be taken in the supine position and will include BP and HR, sitting or standing BP and HR, RR, and body temperature. . Sitting or standing measurements will be taken within approximately 5 minutes of sitting or standing.

c. For women of child-bearing potential, on-site with urine pregnancy test kit. If the on-site UPT is positive, a serum pregnancy test will be done. For post-menopausal women <60 years or of age, a serum FSH will be done at the screening visit only.

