- Dizziness defined as lightheadedness or fainting on rising from lying to sitting or standing that limits instrumental ADL and severe enough to indicate non-urgent medical intervention within 24 hours of taking study medication/placebo.

It is anticipated that all subjects receiving active treatment will exhibit a prokinetic effect at a dose lower than DLT.

Efficacy:

The primary efficacy objective will be evaluation of the efficacy of repeated daily doses of ENT-01 for up to 25 days in improving the CSBM rate.

A CSBM is a bowel movement where the subject indicated that he/she was “done for the day”, that he/she had “no more poop left to pass” and the bowel movement was not a1 or 2 on the Bristol stool scale and did not occur within 24 hours after taking rescue medication. For each subject, the Fixed Dose period begins on the first day of the subject’s prokinetic dose, (or the highest dose at which the subject did not have a DLT), following the incremental dosing algorithm defined in Section 4.2, Visit 2: Randomization (Study Day1).

Primary Efficacy Endpoint: The primary efficacy endpoint is the change from baseline in the weekly CSBM rate during the Fixed Dose period. Baseline is defined as the weekly CSBM rate during the 2-week screening period. The fixed dose response will be obtained as the weekly CSBM rate during the Fixed Dose period. For each subject, the Fixed Dose period begins on the first day of the subject’s prokinetic dose, (or the highest dose at which the subject did not have a DLT), following the incremental dosing algorithm defined in section 4.2 Visit 2: Randomization (Study Day 0, treatment begins the following day at home).

The frequency of CSBMs will be determined via a web-based electronic diary where the passage of a bowel movement or absence thereof will be recorded daily throughout the study by the subject.

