- Reaches the maximum dose of 10 tablets (i.e., 250 mg for active treatment); or,
- Reaches the dose limiting tolerability(DLT).

If the subject has 4 or more episodes of diarrhea with a consistency of 6-7 (see [APPENDIX 6](#)) within 24 hours of a dose on 2 consecutive days at a given dose, the dose will be reduced by 25 mg and fixed at that dose assuming diarrhea subsides.

Should a prokinetic response not occur at 250 mg (or 10 tablets), subjects will continue to take 10 tablets daily for the remainder of the 25-day treatment period.

During this visit, the following assessments and procedures will be performed:

- Review of Inclusion/Exclusion Criteria
- Confirmation of eligibility: To be randomized to receive double-blind study medication in this study, subjects must meet the following criteria:
 - Have at least 11 ‘Available Data Days’ (days with e-Diary compliance sufficient for determining whether a CSBM occurred) (Subjects with fewer than 11 diary days will continue to fill in their diaries until 11 days’ worth of information is available and randomization will be delayed). Have had fewer than 3 complete spontaneous bowel movements per week based upon the average CSBM rate reported during the 2-week Screening Period. This rate will be calculated centrally with a computer-based system and requested by the site the day before randomization.
 - Be deemed eligible for randomization by the enrollment committee
 - Weight
 - Orthostatic Vital Signs
 - 12-lead ECG

- Pregnancy Testing – For women of child-bearing potential only.
- Randomization: Sites will utilize a centralized, computer-based system (IWRS) to obtain the randomization bottle (s) assigned to each subject.
- In-clinic Levodopa Dosing – Subjects will take their morning dose of levodopa in the clinic.
- Subjects will be given study medication and will take their first dose the following day at home, on an empty stomach. The day after Visit 2 will be the first day of treatment.
- Levodopa PK Draws – The first daily dose of L-Dopa will be administered in clinic. Blood samples will be obtained pre-L-Dopa dose and at 20, 40-and 60-minutes post-dose. (Applicable to the levodopa PK sub-study only.)
- Dispense Rescue Medication, as needed. Subjects continue appropriate use of rescue medication, ensuring adequate bowel movements every 3 days.
- AE Review
- Prior and Concomitant Meds
- C-SSRS

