5.4 Exclusion Criteria

1. Unable or unwilling to provide informed consent or to comply with study procedures.
2. Diagnosis of secondary constipation beyond that of Parkinson's Disease

3. Review of Screening Diaries indicates either of the following:

- Fewer than 11 days of diary completion and/or
- More than 3 complete spontaneous bowel movements per week based upon the average CSBM rate reported during the Screening Period.

4. A compromised gastrointestinal system which includes:

- Structural, metabolic, or functional GI diseases or disorders
- Acute GI illness within 2 weeks of the screening visit
- History of major GI surgery within 30 days of the screening visit (a history of cholecystectomy, polypectomy, hernia repair or appendectomy are not exclusionary as long as they were performed more than 30 days before the screening visit)

5. Unable or unwilling to withdraw from laxatives, opiates, clonazepam, or any medications which may cause constipation, 2 weeks prior to the dose adjustment period and throughout the rest of the study.

6. Unable or unwilling to withdraw from proton pump inhibitors and antacids at the end of the screening period.

7. Any clinically significant abnormalities on screening laboratories or physical examination requiring further evaluation or treatment.

8. Neurological disorder other than Parkinson's Disease that in the opinion of the investigator might interfere with the conduct of the study.

9. On treatment with intra-jejunal dopamine or carbidopa/levodopa (i.e. Duopa).

10. Subjects starting a new Parkinson's Disease medication or modifying an existing medication within 2 weeks prior to enrollment.

11. Unable to maintain a stable diet regimen.

12. Subjects with a cognitive impairment that preclude them from understanding the informed consent.

13. Subjects placed under legal guardianship.

14. Females who are pregnant or breastfeeding.
15. History of excessive alcohol use or substance abuse.
16. Participation in an investigational drug trial within the month prior to dosing in the present study.
17. Any other reason, which, in the opinion of the investigator, would confound proper interpretation of the study.

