2.6. Efficacy, Pharmacokinetic, Safety and Tolerability Endpoints

2.6.1 Efficacy Endpoints

Primary Efficacy Endpoint

The primary efficacy endpoint is the change from baseline in the weekly CSBM rate during the Fixed Dose period.

Baseline is defined as the weekly CSBM rate during the 2-week screening period. If a subject has more than two weeks of entries during the screening period, consecutive missing entries during the screening period will be excluded from baseline calculations, and the last fourteen days with entries during the screening period will be used to derive baseline weekly rates.

Subjects with fewer than 11 days of diary data during screening would be excluded from the study. The primary efficacy endpoint will be obtained as the weekly CSBM rate during the Fixed Dose period with exceptions as noted in section 4.7. The frequency of CSBMs will be

determined via a web-based electronic diary where the passage of a bowel movement or absence thereof will be recorded daily throughout the study by the subject.

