3. SUBJECT POPULATIONS

3.1. Population Definitions

The following subject populations will be evaluated and used for presentation and analysis of the data:

- **Safety Population:** The Safety Population will consist of all subjects who receive at least one dose of study medication during the study. Subjects will be analyzed based on the treatment that they actually received. All safety analyses will be based on this population.
- **Modified ITT Population:** The modified Intent-to-Treat (mITT) Population will include subjects who are randomized and have the stool diary assessments both at baseline and at least one post baseline time-point. Subjects who are found later to have inclusion/exclusion violations will be excluded from the mITT population.
- **Fixed Dose Population:** The Fixed Dose Population will include all subjects who are in mITT Population who enter the Fixed Dose period of the study and are in the treatment period for at least seven days, not including the date of randomization.
- **Efficacy Evaluable Population:** The Efficacy Evaluable Population will include subjects who are in the Fixed Dose Population, complete the Fixed Dose period, are compliant with study medication in the Fixed Dose period, and have no major protocol deviations.
- **Pharmacokinetics Population:** Pharmacokinetics Population will include subjects with a least one L-Dopa PK result.

The precise reasons for excluding subjects from the Efficacy Evaluable Population will be fully defined and documented prior to the unblinded interim analysis.

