A patient’s CSBM weekly rate over a particular period will be derived using the following algorithm:

Weekly CSBM Rate = $7 \times \{\# \text{ of CSBMs in the period}\} / \{\# \text{ of days in the period}\}$

The weekly SBM rate calculations use the same algorithm.

If a patient is missing BM information for a day, it will be assumed that the patient had 0 SBMs and 0 CSBMs for that period (with the exceptions in calculating Baseline CSBM and SBM rates noted in Section 2.6).

If a subject diary has “repeat” stool data (eg, a BM repeated with the same date/time of BM) only the latest duplicate observation relative to when the patient entered the data into the diary will be used.

For the calculation of the Baseline CSBM (SBM) weekly rate:

- If the patient has more than 14 days of diary data during the Screening Period, only the last 14 days with non-missing diary entries prior to the randomization visit will be used (i.e., the days which are more than 14 days prior to the randomization visit will be excluded)
- If a patient has 11- 14 days of diary data, all available diary days will be used.
- If a subject has more than two weeks of entries during the screening period, consecutive missing entries during the screening period will be excluded from baseline calculations, and the last fourteen days with entries during the screening period will be used to derive baseline weekly rates.

For analyses of the CSBM (SBM) in the Fixed dose period, if a patient has not been in the Fixed Dose period for at least seven days, then the number of days used for calculating the weekly CSBM (SBM) rate will be adjusted to seven days by using the last “n” days of the Dose Escalation period leading up to the fixed dose period to get to 7 days in the Fixed Dose period. This derivation will be used for all efficacy endpoints for the Fixed Dose Period (e.g., stool ease of passage and stool consistency).

For analyses of the CSBM (SBM) rate during the single-blind placebo and washout periods, all available data in those periods, excluding observations on the date of the single-blind placebo visit as described before, will be used in the derivations of weekly rates described at the beginning of this section.

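### Eligibility, stratification and analysis share neither one stated baseline window nor one upper limit for the CSBM rate, and SAP 3.1 removes later-found eligibility violators from mITT

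*Protocol*

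**What the plan says.** **Eligibility window.** Protocol Table 1, footnote a (repeated in Appendix 2 and SAP Table 1), requires a rate below 3 per week "based upon the average CSBM rate during the first 2 screening weeks (baseline period"). Exclusion 3 (synopsis and section 5.4) uses a different span: "More than 3 complete spontaneous bowel movements per week based upon the average CSBM rate reported during the Screening Period". Section 4.2 refers to a two-week screening period without saying which two weeks, and adds: "This rate will be calculated centrally with a computer-based system and requested by the site the day before randomization".

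**Analysis window.** Protocol 3.1: "Baseline is defined as the weekly CSBM rate during the 2-week screening period". SAP 2.6.1, where there are more than two weeks of entries: "the last fourteen days with entries during the screening period will be used to derive baseline weekly rates". SAP 4.6.1 agrees ("only the last 14 days with non-missing diary entries prior to the randomization visit will be used") and adds for shorter diaries: "If a patient has 11- 14 days of diary data, all available diary days will be used".

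**Length of screening.** Protocol 4.1 runs screening from Day -21 to Day -1. Visit 2 is Day 1 with +8 days in section 4.2, but +/-8 days in Table 1, Figure 1 and Appendix 2. Margin comments left in the text ask which applies. The SAP schedule still starts at Day -14, with Visit 2 at Day 1 +/-2 days in its Table 1.

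**Upper limit.** Fewer than 3 per week: synopsis inclusion 8, footnote a, sections 4.2 and 5.2. Exactly 3.0 admitted: inclusion 8 in section 5.3, exclusion 3, the 1.0-3.0 stratum, and SAP 2.2, which records that 2.9 became 3.0 for the second part.

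**Consequence for the analysis sets.** SAP 3.1: "Subjects who are found later to have inclusion/exclusion violations will be excluded from the mITT population". The Fixed Dose Population is drawn from mITT, and SAP 4.6.3 defines success on it.

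**The concern.** With 14 days of screening, the first two weeks, the last 14 days and the whole period are the same days. The SAP schedule still describes that design. Under the amended protocol they are three different spans, and a fully compliant subject can have three different baseline rates.

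Two things are at stake. First, a subject who was properly randomized under one passage can be called an eligibility violator under another. SAP 3.1 then takes that subject out of mITT, and so out of the set on which success is judged. The SAP requires reasons for exclusion from the Efficacy Evaluable Population to be documented before the unblinded interim analysis, but sets no such deadline for removals from mITT.

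Second, the baseline CSBM strata enter the secondary and exploratory ANCOVA models, the stratified log-rank tests, the CMH tests, the linear trend model and the subgroups. SAP 4.2 speaks of the randomization strata, but the SAP never says whether these are read from the IWRS or rebuilt from the diary. If rebuilt, they need not match the strata used to randomize.

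**Working it through.** The documents give no reclassification rate, so there is no stated figure to reproduce.

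**Step 1: overlap of the windows.** With S screening days, all with diary entries, the first 14 and last 14 days share max(0, 28 - S) days.

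- S = 14: 14 days shared
- S = 21: 7 shared
- S = 25: 3 shared
- S = 28 or 29: none shared

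The +8 reading gives S = 21 to 29, the +/-8 reading gives 13 to 29, and the SAP schedule gives about 12 to 16.

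**Step 2: how easily the stratum flips.** In 14 days, 0-0.9 per week means 0 or 1 CSBM and 1.0-3.0 means 2 to 6. One CSBM can move a subject across the cut.

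**Step 3: hand calculation.** The only baseline mean in the documents is 1.2 per week (Phase 2a, Protocol 2.2), with no SD. Assume first that every subject has that rate and that counts are Poisson. For S = 21, let A, C and B be the first, middle (shared) and last 7 days, each with mean 1.2.

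- P(0) = e^-1.2 = 0.3012; P(1) = 0.3614; P(0 or 1) = 0.6626.
- Low in the first window and high in the last, with C = 0, A of 0 or 1, B of 2 or more: 0.3012 x 0.6626 x 0.3374 = 0.0673.
- The same, with C = 1, A = 0, B of 1 or more: 0.3614 x 0.3012 x 0.6988 = 0.0761.
- Sum 0.1434. The reverse is equally likely, so 2 x 0.1434 = 28.7%.

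For S = 28, p = e^-2.4 x (1 + 2.4) = 0.3084, and 2p(1 - p) = 2 x 0.3084 x 0.6916 = 42.7%.

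**Step 4: the same calculation with spread between subjects.** Subject rates are gamma-distributed. Subjects have 0-6 CSBMs in the first window, and the rates are scaled so that these eligible subjects average 1.2 per week. Entries are the % whose stratum differs between the two windows.

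| Assumed rates | S=14 | S=15 | S=16 | S=21 | S=25 | S=28-29 |
|---|---|---|---|---|---|---|
| Same for all | 0 | 6.6 | 11.9 | 28.4 | 36.8 | 41.7 |
| Gamma, shape 4 | 0 | 5.5 | 10.0 | 24.0 | 31.0 | 35.2 |
| Gamma, shape 2 | 0 | 4.9 | 8.8 | 21.0 | 27.1 | 30.7 |
| Gamma, shape 1 | 0 | 4.0 | 7.2 | 17.3 | 22.2 | 25.1 |
| Range, mean 0.8-1.6, shape 0.5 to constant | 0 | 3.2-6.8 | 5.8-12.5 | 14.2-31.8 | 18.5-42.6 | 21.0-49.9 |

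The range row omits shape and mean pairs that cannot produce that eligible mean.

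**Step 5: subjects exposed to removal.** Exactly 3.0 on 14 diary days means 7 x 6/14, that is 6 CSBMs. The share is P(6)/P(0 to 6). Over the four mean-1.2 rows it is about 3 to 9%. The share with 0-6 CSBMs in the first window but 7 or more in the last is about 1 to 8% at S = 21 and 1 to 12% at S = 28-29.

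**The case against.** A reader might infer that a fifth to a third of subjects will change stratum. The documents do not support that. The stratum is fixed at randomization. Footnote a is an eligibility rule, and its baseline-period label is the only link to the strata. Section 4.2 has the rate calculated centrally and requested the day before randomization, which fits the last 14 days equally well. If the IWRS uses those days, the mismatch is 0%.

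A reader might also take 21 to 29 days of screening as settled. That is only the section 4.2 reading. Further, the reason section 4.2 gives for delaying randomization is a diary with fewer than 11 days. Subjects extended for that reason would have about 11 diary days, all of which are used, so the 25- and 28-29-day columns do not describe them.

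Nor do the documents support a claim that the primary result is biased. The ANCOVA in SAP 4.6.3 uses the continuous baseline rate, derived identically in both arms. SAP 4.2 already points towards the randomization strata. No passage orders eligibility to be retested on the SAP window, and the limit conflict looks like incomplete updating after 2.9 became 3.0.

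All of this limits the size of the point. It does not remove the contradictions: the passages disagree on window and limit, the IWRS window is unstated, and SAP 3.1 attaches a consequence to an eligibility violation.

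**Conclusion.** The point holds as a contradiction to be reconciled before unblinding. It reaches the primary analysis set through SAP 3.1. A subject at exactly 3.0, or eligible on one window only, could be removed after randomization because of document wording alone. That is a possibility, and the documents do not show that it has happened. The step 5 shares indicate how many could be exposed under the assumed rates.

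For the strata, the size is conditional. If the IWRS uses the first 14 days and the SAP strata are rebuilt from the diary, about 14-32% of fully compliant subjects would be classed differently at 21 days and 21-50% at 28-29 days. These figures rest on an assumed rate distribution, since the documents give a mean and no spread. The mismatch is 0% if the IWRS uses the last 14 days, or for any subject with 14 or fewer diary days. The primary ANCOVA is not directly affected by the stratum.

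**What to change.** - Reconcile Protocol Table 1, sections 3.1, 4.2 and 5.2-5.4, the synopsis, Appendix 2 and SAP Table 1, 2.6.1 and 4.6.1 to one 14-day window, used for eligibility, stratification and analysis, and to one upper limit.
- Settle the Visit 2 window, close the margin comments, and bring the SAP schedule into line with the protocol.
- Record from the IWRS specification which days feed the stratum.
- State in the SAP that all strata-adjusted models, stratified tests and baseline subgroups use the stratum as randomized in the IWRS.
- State in SAP 3.1 that no subject leaves mITT for an eligibility difference created only by the choice of window or limit.
- The starting tablet number is tied to the same baseline, so those passages must be reconciled as well.

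The cost is wording. The IWRS already holds the as-randomized stratum, and no new data are needed.
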